A randomized control design will be used to test the efficacy of the CHW intervention to improve HTN control among South Asian individuals with diabetes in Atlanta. The intervention will recruit participants from three clinical sites in Atlanta, GA: 1) The Emory Family Medicine Clinic is located in North Atlanta and serves approximately 1,200 unique South Asian patients annually; 2) Grady Clinic at Brookhaven is a safety net county clinic that sees a high volume of low-income South Asians (approximately 6,000 per year; 3). The Shifa Free Clinic is a community-based free clinic coordinated by the Islamic Circle of North America, Atlanta branch, to serve uninsured and under-insured South Asians in Georgia.. On average, they see 200 unique South Asian patients per month at each site. Both Emory Family Medicine Clinic and Grady Clinic utilize EHR systems which will be used to generate lists of eligible patients for the intervention. Shifa Clinic is currently transitioning to an EHR system, thus patient data will be electronically accessible for patient recruitment and follow-up outcome data. Each of the sites has expressed interest and commitment to participating in the study. The community centers will not be engaged in research, all consenting and procedures will be completed by Emory study staff.

We also anticipate enrolling participants from community-based recruitment with the CHWs referring participants that they meet at South Asian community events and advertising the study. The proposed research design is a modified stepped wedge design, whereby 2 groups will implement the intervention in phases. The time prior to the intervention will serve as the comparison group. Enrolled patients will be randomized to treatment (Group A) and wait-list control (Group B) groups within each site.

There are five primary research groups for this study: 1) 326 treatment participants who will receive the CHW intervention; 2) 326 control participants who may receive the CHW intervention as a point of service at a later point; 3) 10 subjects who will participate in provider surveys; 4) 25 subjects who will participate in qualitative key informant interviews; 5) a retrospective EHR review of characteristics of South Asians seen at Emory Healthcare and NYU hospital system between 2014 and 2019; and 6) 50 subjects who will participate in focus groups.

B2. CHW Component:

1. Data collection and consenting with treatment participants

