Clinic to sign the consent form and complete the baseline survey. Control participants will not be contacted during the intervention and will only be contacted once the intervention with treatment participants has been completed; those who were control in the first wave of recruitment can then be enrolled in the second wave. Due to the study funding period, those in the second wave control arm will be offered education sessions as a point of service and not as part of research.

CHW Intervention Period

There is a 6-month intervention period immediately following recruitment. Each session will be held multiple times throughout the month to accommodate a variety of schedules by the treatment participants. Month 1 has participants coming to Session 1 followed by one follow-up phone call. Month 2 has participants coming to Session 2 followed by one follow-up phone call and then one in person visit at the participant's home or at local meeting point used for a session. Month 3 has participants coming to Session 3 followed by two follow-up phone calls within the month. Month 4 has participants coming to Session 4 followed by one follow-up phone call and then one in person visit at the participant's home or at local meeting point used for a session. Month 5 has participants coming to Session 5 followed by two follow-up phone calls within the month. Month 6 concludes the intervention period with an endpoint survey and completion certificate.

Provider Surveys

Over the course of 2 months, providers at participating practices will be invited to complete the Provider Survey via email link. Paper surveys will also be available for those who prefer to fill out the survey in hard copy. No undue pressure will be given to subjects for participation as the participation is entirely voluntary and will be described via email or verbally to the invited participants (See Invitation Script and Elements of Informed Consent for Provider Survey).

Key Informant Interviews

Over the course of 2 months, participating providers and community health workers will receive an invitation to participate in the interview (See Invitation Script and Elements of Informed Consent for Key Informant Interview). No undue pressure will be given to subjects for participation as the participation is entirely voluntary (See Verbal Consent Script for Key Informant Interview).

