During the study period, the research team will be performing a retrospective chart review of South Asians, using surnames to identify patients of South Asian origin. We will submit a waiver of consent to obtain these records.

VII. DATA COLLECTION AND ANALYSES

A. PHASE 2: Data collection and implementation of the CHW intervention (recruitment, consenting, CHW led education sessions) will be led by Emory University. All participants will attend Session 1. Everyone who attends will receive a unique study identifier that will associate a specific study number with the participant. This information will then be downloaded onto the NYU servers into R statistical software for randomization. We will use stratified randomization by age and gender to assign patients to intervention or control arms.. The table necessary to link patient identifiers and the study ID will be maintained by the Emory-based study coordinator to ensure that patient confidentiality is maintained.

Treatment Participants

The study ID will be used for all implementation activities and reporting on CRFs. Thus, patients who are observed more than once will have the same study ID in each extract, which is necessary for the planned analyses. Study data will be collected in the form of a survey at baseline and at endpoint. Follow up calls and visits will also be recorded in REDCap, or paper-based CRFs and kept in locked boxes until transport back to the Emory Dunwoody offices for input into REDCap and secure storage.

A random sample (n=50) of less engaged and more engaged previously enrolled treatment group participants of the CHW intervention will receive an invitation to participate in the focus group. This will be a one-time anonymous audio-recording with no follow-up; no names or identifying information will be collected at the time of the focus group.

The focus group will be completed in-person or virtually via Zoom (Emory University has HIPAA compliant Zoom accounts which have been institutionally approved for telemedicine, see supporting documentation) to accommodate the current COVID-19 situation. The method (face-to-face vs. virtual) will be determined at the discretion and preference of the participants, while following institutional regulations for COVID-19. Recordings will only include audio (not video).

Control Participants

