B3. Sampling. Across the three clinical sites, there will be approximately 3,600 unique South Asian patients that have had an office visit in the last year. Based on preliminary analysis of [name] patient panel, we estimate 30% of those individuals will have a Type II Diabetes diagnosis (n=1080), and estimate that 60% will have co-morbid diabetes and HTN (n=648), 75% of these individuals will have uncontrolled HTN (n=486), and additional 5% will be excluded due to not meeting other eligibility criteria, leaving 462 individuals eligible for the study. Of these individuals, approximately 50% will be randomized to the treatment group, and we estimate based on our previous studies that 40% of patients will be interested in the study and consent to enroll into the study (n=326). Based on retention rates from our CHW studies,^{12,95,96,98,128,129,131} we estimate that approximately 90% of individuals in control and treatment quarters will be followed up at six months (n=83). Thus, across sites, we will enroll approximately 652 patients per six-month period, resulting in total recruitment of approximately 326 treatment group participants across 3 practice sites. Treatment group participants will be matched to 326 control group participants. Approximate CHW caseload over a six-month period is 16 participants for a full-time CHW.

Specific Aim 3 Analysis.

B4. Analysis to address this aim will be guided by the questions in **Table 4**.

Table 4: Guiding Questions

Utilization Patterns	
 • How frequently do clinicians utilize the intervention? • What is the percentage of adoption? • Does the utilization pattern change over time?
Physician Attitudes Regarding the Integrated Intervention	
 • What are physicians' attitudes regarding CHW approaches to diabetes and HTN management? • How satisfied are the physician's with the integrated intervention tools? • What are the barriers and facilitators of using the CHW integration components? • How does the intervention affect clinicians' satisfaction with workflow around T2DM management?

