All study personnel will have completed the mandatory CITI human subjects research training before commencing any study-related activities.

The informed consent form for this study has been created by the NYU School of Medicine Office of Science and Research in accordance with Federal guidelines, including the Health Insurance Portability and Accountability Act (HIPAA).

CHW Treatment Participants

All potential treatment participants will receive a copy of the study consent form by the CHW. The format of the consent form consists of a 1-page consent signature form with an accompanying brochure fully detailing all components of the full informed consent (See Consent Brochure and Consent Signature Page for CHW Intervention and Key Information Sheet). This layout is more appropriate for clinic-based and community-based recruitment. First, based on our experience in previous community-based studies, community members were discouraged by a multiple-page consent form, and we expect the same in a clinic setting. Even though this format provides the same exact information as the standard consent form, we expect that it will be less intimidating for participants who are learning about the study in a community-based recruitment atmosphere.

Consent processes will be conducted in a manner that maximizes confidentiality and privacy and allows questions to be asked. Eligible patients demonstrating interest in participating in the project will meet with a study team member who will explain the intervention and consent form and invite them to sign a consent form. Consent will be obtained in a closed room, on a one-on-one basis. Participants are free to withdraw from participating in the study at any time without repercussions. Participants will be advised during the consent process that they have the right to withdraw entirely and that their refusal will not jeopardize their relationship with their CHW or primary care physician.

Provider Surveys

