To determine that the subject or his/her authorized representative understood the information presented, they will be given opportunity to ask questions before giving consent to participate. They can also choose at that time not to be in the study. The individuals authorized to obtain consent will do so by presenting to the subjects the consent form and will verbally read along with the subject and explain the study. The individuals will explain the purpose of the study, the procedures, possible risks and anticipated benefits, that it is voluntary, and how to withdraw if they choose to at a later time. Limited English speaking individuals will be given a translated consent form, and Bengali/Urdu/Punjabi-speaking personnel will obtain consent from them.

D. Debriefing Procedures.

Information will not be withheld from the subjects related to their participation in the study.

E. Consent Forms. Eligible treatment patients will be consented and enrolled to participate in the study (see Consent Brochure/Signature Page for CHW Intervention).

F. Documentation of Consent

Informed consent will be documented by the use of a written consent brochure/signature page to be signed and dated by the subject or the subject's legally authorized representative at the time of consent (See Consent Brochure and Consent Signature Page for CHW Intervention) for all those participants enrolled in the CHW intervention. Individuals authorized to obtain consent will read the consent form to the subject or the subject's legally authorized representative, and the subject or representative will be given adequate opportunity to read it and clarify questions before it is signed. The subject will receive a copy of his/her signed consent form. A translated written consent form will be used for non-English speaking subjects, depending on their preferred language. The informed consent will outline elements of the EHR data collection, CHW group education, one-on-one counseling and survey data collection.

Baseline surveys will also be conducted by Emory study staff with participants within two weeks after consent. The same survey will be completed with intervention participants approximately six months after the start of intervention to evaluate the effectiveness of the CHW intervention, the CHW Intervention 6-month survey will be completed at the last education session.

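### The documents contradict themselves on whether patients consent before or after they are allocated to an arm

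*Combined protocol and SAP*

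**What the plan says.** **Text that puts consent first**

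- III.B1 (Phase 2 design): "Enrolled patients will be randomized to treatment (Group A) and wait-list control (Group B) groups within each site".
- III.B2: a signed consent form is a condition of taking part, and surveys, which include BP, are collected from everyone at baseline and six months.
- VI.A (CHW Screening Period): all participants are sent an invitation letter, and those who agree sign consent and complete the baseline survey at the clinic.
- VII.A (Phase 2): "All participants will attend Session 1". Attendees receive a study ID. "This information will then be downloaded onto the NYU servers into R statistical software for randomization", stratified by age and gender.
- VII.A (Control Participants): controls complete both surveys and Session 1, and are left alone for the remainder of the six months.
- Consent section, F (Documentation of Consent): written consent covers everyone enrolled in the CHW intervention. V.A counts that enrolment as 652, of whom 326 are controls.

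**Text that puts allocation first**

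- VII.B3 (Sampling): of 462 eligible patients, "approximately 50% will be randomized to the treatment group, and we estimate based on our previous studies that 40% of patients will be interested". Later: "Treatment group participants will be matched to 326 control group participants".
- III.B2: physicians are given a list of patients eligible for the treatment arm so that they can refer them. The contact log covers eligible members of the treatment group, and its status codes include declined and not reached.
- VI.A: "Control participants will not be contacted during the intervention and will only be contacted once the intervention with treatment participants has been completed".
- Consent section: "All potential treatment participants will receive a copy of the study consent form by the CHW" and, under E (Consent Forms), "Eligible treatment patients will be consented and enrolled to participate in the study".

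The analysis section (VII.B1) defines the treatment indicator by randomised arm but names no analysis set.

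**The concern.** The order of consent and allocation decides who is compared with whom. If consent and baseline come first, both arms have passed the same filter and the comparison is randomised. If patients are allocated first and consent is sought in the treatment arm, 60% of that arm drops out by choice, while the control arm may not be filtered at all. Two things can then happen:

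- Consenters are compared with controls not selected by consent. Any difference between people who accept and people who decline is mixed with the CHW effect.
- Everyone is analysed as assigned. That removes the selection bias but averages the effect over people who never received the intervention.

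Staff working from III.B1 and VII.A would run a different trial from staff working from the list wording in III.B2, the no-contact sentence in VI.A and VII.B3. Selection at recruitment cannot be undone at analysis.

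**Working it through.** **1. Does the plan's arithmetic show which order is meant?** Inputs from VII.B3: 3,600 patients, 30% with diabetes, 60% of those with hypertension, 75% of those uncontrolled, 5% excluded, 50% to treatment, 40% consent, 90% followed up.

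- Eligible: 3,600 × 0.30 × 0.60 × 0.75 × 0.95 = 461.7, stated as 462.
- Allocate, then consent: 462 × 0.5 = 231; 231 × 0.4 = 92.4; 92.4 × 0.9 = 83.2.
- Consent, then allocate: 462 × 0.4 = 184.8; 184.8 / 2 = 92.4; 92.4 × 0.9 = 83.2.

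The stated n=83 reproduces both ways, so it cannot settle the order. The n=326 attached to the consent step reproduces neither way: the chain gives about 92, and 326 / 231 = 141% of the patients in the treatment half.

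**2. The planned effect.** Inputs from VII.B2: 15% v 35%, two-sided 0.05, 81 per arm, 10% loss. Power = Φ{[d√n − 1.96√(2p̄(1−p̄))] / √(p₁(1−p₁) + p₂(1−p₂))}, where d = p₂ − p₁ and p̄ is their mean. At 81 × 0.9 = 72.9 evaluable per arm this gives 80.3%, which matches the claim of more than 80%.

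**3. Allocation first, everyone analysed as assigned.** Assumptions: 40% uptake, no effect in non-consenters, 90% follow-up in both arms.

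- Treatment arm rate: 0.4 × 35% + 0.6 × 15% = 23%. Difference: 23% − 15% = 8 points.
- At 231 × 0.9 = 208 per arm: [0.08 × √208 − 1.96 × 0.555] / 0.552 = 0.12, so power is about 55%.
- At 231 per arm with no loss, power is 59%. If the 326 per arm were instead the number allocated before consent, 326 × 0.9 = 293 evaluable gives about 70%.
- For 80% power: 377 evaluable per arm, or 377 / 0.9 = 419 allocated.

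**4. Allocation first, consenters compared with controls not selected by consent.** The documents give no figure for how consenters and non-consenters differ, so the inputs here are assumptions. Hold the untreated rate at the planned 15% overall. If non-consenters would reach pₙ untreated, consenters would reach p_c = (0.15 − 0.6pₙ) / 0.4. With no true effect, the spurious difference is p_c − 0.15:

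- pₙ = 15%: p_c = 15%, difference 0.
- pₙ = 12%: p_c = 19.5%, difference 4.5 points.
- pₙ = 10%: p_c = 22.5%, difference 7.5 points.
- pₙ = 8%: p_c = 25.5%, difference 10.5 points.

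For the last three, the chance of a significant result favouring treatment at 83 per arm is about 12%, 23% and 39%, against a nominal 2.5%. The sign could also reverse: pₙ = 18% gives p_c = (0.15 − 0.108) / 0.4 = 10.5%, a difference of −4.5 points.

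**The case against.** The case for consent first is substantial. The design section, the general consent and survey statements in III.B2, the invitation sentence in VI.A and the only description of the randomisation procedure (VII.A) all agree with it. The written-consent clause covers everyone enrolled in the CHW intervention, and V.A includes the controls in that number. A reader might infer from the treatment-only wording elsewhere that controls give no consent and have no study baseline BP; these passages do not support that.

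The VI.A sentence on contacting controls follows directly on the consent and baseline step, and can be read as no contact after baseline. The Control Participants text in VII.A says so. VII.B3 is a feasibility estimate, not a procedure, and its 40% refers to patients, not to treatment-arm patients. A reader might infer from it that only treatment-assigned patients are approached, but the sentence does not say that.

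All of this stands, and it makes consent first the likelier intention. It does not remove the conflicting text. The contact log in III.B2 is the hardest to explain away: a member of the treatment group can be recorded as declined or not reached only if the label precedes consent. The VI.A sentence carries no qualifier of its own, arms randomised after consent need no matching, and no section is given precedence.

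**Conclusion.** This is an internal inconsistency about the primary comparison, and it should be corrected. A reader might go further and infer that the randomised comparison is broken. The documents do not support that: the harm arises only if allocation before consent is what is carried out, and its form then depends on an analysis set that the plan does not define.

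Under that condition, the dilution is from 20 points to about 8, with about 55% power at 208 evaluable per arm. This rests on the plan's own 15%, 35% and 40%, plus the assumption of no effect in non-consenters; 231 allocated per arm is implied by the sampling chain and is not a stated analysis set. The selection bias is of unknown size and sign, and the 0 to 10.5 points shown is an illustration. Under consent first, neither harm arises.

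**What to change.** State one sequence consistent with III.B1 and VII.A: screening, written consent and baseline BP for all, Session 1 where VII.A already places it, randomisation, and analysis of all randomised participants as assigned. Then align the rest:

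- III.B2: describe the physicians' list and the contact log as covering *eligible patients*, without an arm label.
- VI.A: qualify the no-contact sentence to agree with VII.A, so that controls are not contacted after baseline and Session 1 until the endpoint survey.
- VII.B3: apply the 40% consent rate to the 462 eligible before the 1:1 split; replace *matched to* with *randomised 1:1 with*; and reconcile n=326 with the roughly 92 per arm that the chain yields. Correcting the order does not by itself resolve that mismatch.
- Consent section (CHW Treatment Participants, and E): make the text cover both arms.
- VII.B1: name the analysis set.

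The cost is an amendment to wording. The consent-first text already provides for consent and a baseline survey in both arms, so no visit, measurement or participant is added.

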We will conduct cross-sectional analyses, using EHR-based samples South Asians aged 18+ years living in the greater Atlanta and New York City areas from two large healthcare systems. Prevalence values and 95% CIs will be estimated by study site, sex, age-group, and BMI category. Participant characteristics will be stratified by sex and compared by study using χ^2 test or ANOVA as appropriate. The non-normally distributed variables of fasting and 2-h plasma glucose will be log transformed. The effect of location of residence (Atlanta or New York) on the risk of diabetes and prediabetes will be assessed using standardized polytomous regression. Initially, an unadjusted regression model will be created to compare the individual association between study location and prevalence of diabetes and prediabetes. Subsequent multivariable models were then created to adjust for covariates including age, sex, blood pressure, BMI, and educational status. All analyses will be performed using SAS, version 9.4 (SAS Institute, Cary, NC).

B2. Power Calculation.

We conservatively estimate a 20% difference in effect size (i.e., BP control) when comparing intervention and control group participants. Our power calculation was based on our previous studies. Based on results from these studies, at six-month follow-up we conservatively assume a 15% BP control rate for the control group and 35% BP control rate for the treatment group. In our previous work, BP control rates at baseline varied; however, in the proposed study all participants will have uncontrolled BP at baseline. Further, in our past work control group participants experienced almost no change in BP control at follow-up; here we conservatively estimate a 15% BP control rate at follow-up. Accrual of 162 participants, evenly randomized to intervention or control groups, will provide greater than 80% power to detect this difference, using a 2-sided, 0.05-level test (i.e., approximately 81 intervention and 81 control participants). These calculations assume a 10% loss to follow-up.

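### Section VII.B3: the recruitment funnel yields about 92 treatment participants, not 326; 326 enrolled cannot go with 83 followed up, and the 652 target has no stated derivation

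*Combined protocol and SAP*

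**What the plan says.** Section VII.B3 (Sampling) starts from "approximately 3,600 unique South Asian patients that have had an office visit in the last year". It applies 30% with type 2 diabetes (1,080), 60% of these with hypertension as well (648), 75% of these uncontrolled (486) and a further 5% excluded, "leaving 462 individuals eligible for the study". About half go to treatment, and "40% of patients will be interested in the study and consent to enroll into the study (n=326". It then expects that "90% of individuals in control and treatment quarters will be followed up at six months (n=83", and concludes that "we will enroll approximately 652 patients per six-month period", with about 326 treatment participants across three practice sites.

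Section VII.B2 (Power Calculation) assumes blood pressure control of 15% in the control group and 35% in the treatment group, a two-sided 0.05 test and 10% loss to follow-up: "Accrual of 162 participants, evenly randomized to intervention or control groups, will provide greater than 80% power to detect this difference".

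Sections III.B1 and V.A give 652 (326 per arm) as the enrolment of the whole trial; V.A adds that this allows for 10% attrition. Section III.B1 names community-based recruitment as a further source, and V.A admits self-reported diagnoses from that route. Section VI.A and the control-participant text of VII.A describe a second wave that first-wave controls may enter. None of these sections gives an expected number for either route.

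**The concern.** Every step of the funnel can be checked down to 462, and then the chain breaks. The 326 exceeds the whole treatment half of the eligible pool, and the 83 that follows belongs to a different, smaller enrolment. A reader cannot tell whether the sponsor expects about 83 or about 293 patients per arm at six months, or whether 652 is a total or a six-monthly rate. The target is also about four times the number in the only power calculation (652 / 162 = 4.0), and no reason is given. At stake are the credibility of the recruitment projection and a clear statement of how many patients will be enrolled and analysed.

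**Working it through.** **Funnel (all inputs from VII.B3)**

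- 3,600 x 0.30 = 1,080; x 0.60 = 648; x 0.75 = 486; x 0.95 = 461.7. The plan's 462 reproduces.
- Treatment half: 462 x 0.50 = 231.
- Consenting: 231 x 0.40 = 92.4. The plan prints 326.
- Both arms: 462 x 0.40 = 184.8, about 185.
- Followed up per arm: 92.4 x 0.90 = 83.2. The plan's 83 reproduces, but only from 92.
- From the printed 326: 326 x 0.90 = 293.4, about 293.

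**Can 326 be rescued?**

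- Full consent gives 231; 326 / 231 = 1.41.
- Without the 50% split, the result is 185.
- The nearest match is 648 x 0.50 = 324, which skips the uncontrolled-pressure, exclusion and consent steps, so it is not the calculation described.

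**The total**

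- 652 / 462 = 1.41: B3 enrols more people in six months than it calls eligible.
- At 40% consent, 652 needs 652 / 0.40 = 1,630 eligible people, 3.5 times 462.
- If the clinics supply 185, other sources must supply 652 - 185 = 467.

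**Power (inputs from VII.B2)**

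Two-proportion test, pooled variance under the null, n evaluable per arm:

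power = Phi{ [0.20 - 1.96 x sqrt(2 x 0.25 x 0.75 / n)] / sqrt[(0.35 x 0.65 + 0.15 x 0.85) / n] }

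| n per arm | Origin | Power |
|---|---|---|
| 73 | 81 x 0.90 = 72.9, the B2 figure after loss | 80.3% |
| 83 | B3 as printed | 85.2% |
| 293 | 326 x 0.90 | over 99.9% |

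For n = 83: (0.20 - 1.96 x 0.0672) / 0.0654 = 1.04, and Phi(1.04) = 0.85. B2's 162 (81 per arm) therefore reproduces, with 72.9 rounded to 73.

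**The case against.** The best defence is that B3 is a feasibility paragraph, not the sample-size calculation. That calculation is B2, and it reproduces. Enrolling above the minimum is permissible, and VII.B1 plans subgroup and gender-moderation analyses that a larger trial would serve. This stands: the sample-size calculation is not false, and the endpoint, test and model are untouched. The documents do not, however, give those analyses as the reason for 652.

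A second defence is that community recruitment and the second wave fill the gap. They may, but neither is quantified, and B3 attributes its 326 to the three practice sites. At B3's rates 652 would take about 3.5 passes of 185, and first-wave controls who re-enter add no new people.

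A reader might also infer that the 3,600 contradicts III.B1, where one clinic "serves approximately 1,200 unique South Asian patients annually" and another "sees a high volume of low-income South Asians (approximately 6,000 per year". The documents do not establish that. The 6,000 is not described as unique patients and could count visits, whereas the 3,600 is a count of unique patients. This is a query to the sponsor, not an error.

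**Conclusion.** B3 is wrong as written and should be fixed. On its own inputs it gives about 92 per arm, 185 in total and 83 per arm followed up, against a printed 326 and 652; the overstatement is 3.5-fold (652 / 184.8). The 326 enrolled and the 83 followed up cannot both hold at 90% retention. The six-monthly qualifier on 652 appears only in B3 and conflicts with III.B1 and V.A.

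Two stronger readings are not supported. One is that the trial is underpowered: power for 15% versus 35% exceeds 80% at either 83 or 293 per arm. The other is that 652 is the wrong target: the text shows only that B3 does not derive it and that no other section does. The mismatch may suggest that 326 and 652 were inserted into an older calculation, but the documents do not say so.

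The arithmetic takes B3's percentages at face value. The power figures take B2's 15% and 35% and use the pooled test without continuity correction.

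**What to change.** Restate B3 so that each step follows. With the present inputs: *about 185 of the 462 eligible patients are expected to consent, 92 per arm, of whom 83 per arm are expected to be followed up at six months.* Then choose one target.

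- **If 652 stays:** replace 83 with about 293 per arm followed up. Delete the six-monthly qualifier. Give the numbers expected from community recruitment and from the second wave, counting re-entering first-wave controls once. State in B2 the power at about 293 evaluable per arm (over 99.9% for 15% versus 35%).
- **If the sponsor intends the 162 to 185 that B2 and the funnel support:** correct 652 and 326 in III.B1, V.A and VII.B3.

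The choice is the sponsor's. As a query only, check the 3,600 unique patients against the clinic volumes in III.B1.

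The correction itself restates figures and needs no extra patients. Its downside is a less favourable clinic projection, about 185 rather than 652. Choosing the smaller target also costs sensitivity: from a 15% control rate, the difference detectable with 80% power rises from about 9 points at 293 per arm to 18.5 points at 83, or about 20 points at 73.
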